1. SYNOPSIS

Name of sponsor/company: Xeris Pharmaceuticals, Inc.	
Name of investigational product: Pramlintide-insulin injection (PRAM9)	
Name of active ingredient: Pramlintide acetate and recombinant human insulin	
Study title	A Phase 2, Single-Dose, Randomized, Open-Label, Active-Controlled, Crossover, Pharmacodynamic, and Pharmacokinetic Comparative Study of a Novel Pramlintide-Insulin Co-Formulation in Adults with Type 1 Diabetes Mellitus
Protocol number	DPI-201
No. of study centers	Up to 4 sites in the United States (US)
Clinical phase	Phase 2
Study background	
Most people with diabetes are still unable to achieve glycemic targets with sole insulin therapy alone, particularly after mealtime. Physiologic restoration of the hormonal responses during meals, via pramlintide and insulin, has been demonstrated to reduce postprandial hyperglycemia and to improve blood glucose time in range.
 
The synergy between insulin and pramlintide provides improved glucose control while reducing meal-time insulin requirements. Reduced insulin utilization may also reduce the effects associated with long-term insulin use such as weight gain and higher risks of hypoglycemia.
 
A pramlintide-insulin co-formulation may help reduce the burden associated with co-administration (eg, reduce the number of injections per day). Additionally, co-formulations of pramlintide and insulin may also improve treatment compliance and persistency.

Study rationale	
People with diabetes may have a significant loss of pancreatic beta cell function. This leads to a deficiency of 2 hormones: insulin and amylin. The combined effect of insulin and amylin is to regulate and normalize blood sugar levels.
 
Pramlintide is an injectable drug that closely resembles amylin. Many clinical studies that add pramlintide to insulin have demonstrated improved control of blood sugar.
 
However, the benefits of these products used together also are associated with increased risk of pramlintide-associated nausea and vomiting; increased number of required injections; and tailoring of insulin and pramlintide doses.
 
Xeris Pharmaceuticals has developed a novel, liquid-stable, co-formulation of pramlintide plus regular insulin (PRAM9) that can be delivered as a single, subcutaneous (SC) injection. The fixed dose combination product is expected to allow better management of patient glycemic conditions through improved compliance.

Study objectives	
Primary objective
 
 Evaluate the pharmacodynamic (PD) properties of a single dose of PRAM9 compared to single doses of regular insulin and regular insulin plus pramlintide (co-administered as separate injections) in adults with type 1 diabetes mellitus (T1D)

	
Secondary objectives
 
 Evaluate the safety and pharmacokinetic (PK) profiles of a single dose of PRAM9 compared to single doses of regular insulin and regular insulin plus pramlintide (co-administered as separate injections) in adults with T1D

Study endpoints
	
Primary The PD effects upon plasma glucose levels will be compared between the treatments as defined by the following primary endpoint:
 
 Area under the curve area from administration to 180 minutes (AUC₀₋₁₈₀) (mg/dL × minutes) for plasma glucose > 180 mg/dL 
Secondary Safety:
 
 Incidence of adverse events (AEs), serious adverse events (SAEs) Change from baseline in clinical safety laboratory evaluations (hematology and serum chemistry) Change in vital sign measurements (temperature, respiration, heart rate [HR], and blood pressure [BP]) Change from baseline in body weight Local tolerability assessments (modified Draize Scale and injection site discomfort questionnaires) 
PK/PD: Key secondary endpoints include the following. The full list of secondary endpoints is provided in Section 13.3.2.
 
 Mean proportional time with plasma glucose > 180 mg/dL for 0-180 minutes after study drug administration PK plasma levels (AUC_{0-90 min}, AUC_{0-180 min}, AUC_{0-360 min}, C_{max}, and T_{max}) for both insulin and pramlintide

Study design
	
This is a randomized, open-label, active-controlled, single-dose, 3-treatment, 3-period, 3-way crossover, comparative PD, and PK inpatient study in adults with T1D.


Methodology
	
The study comprises 5 visits: Screening (Visit 1), Treatment Periods (Visits 2 – 4), and Follow-Up (Visit 5).
 
To determine eligibility, subjects will complete the Screening procedures (Visit 1) up to 28 days before the first treatment visit (Visit 2). Subjects will be instructed to eat normally and take their usual medications, but to refrain from alcohol for 24 hours prior to checking in for treatment visits.
 
Treatment periods For Treatment Period Visits 2 through 4, eligible subjects will be instructed to arrive for an overnight stay at the clinical research facility on the day prior to each treatment visit. At the clinic, subjects will be given a standardized dinner meal, and instructed to take their prescribed evening mealtime insulin regimen and basal insulin dose. The subjects will fast after midnight but will be allowed to drink

	
water ad libitum (ie, tap water, bottled water, distilled water, etc. [water without carbohydrates]) and take any prescribed medications.
 
During each Treatment Period Visit (Visits 2, 3, and 4), eligible subjects will receive a single SC dose of PRAM9, regular insulin, or co-administered regular insulin plus pramlintide. On the morning of each treatment visit and prior to dosing, a fasting blood sample will be tested using a blood glucose meter (BGM) to confirm that blood glucose is in the range of 80 to 150 mg/dL.
 
 • If the blood glucose is > 150 mg/dL after repeat test, then the investigator may treat with an intravenous (IV) bolus dose of regular insulin, per discretion, to bring the subject into the required blood glucose range. Before initiating study treatment, at least 40 minutes should have passed from the last dose of administered insulin and the subject's glucose level should be within the range of 80 to 150 mg/dL. • If the blood glucose is < 80 mg/dL after repeat test, then the investigator may treat with oral glucose tabs/solution or IV glucose, per discretion, to bring the subject into the required blood glucose range. Before initiating study treatment, at least 30 minutes should have passed from the last dose of administered glucose and the subject's glucose level should be within the range of 80 to 150 mg/dL. • If the subject's blood glucose cannot be optimized to 80 to 150 mg/dL within 2 hours, then the visit should be rescheduled after a minimum 24-hour wait, per investigator's discretion. 
At Visit 2, once blood glucose is confirmed to be within the range of 80 to 150 mg/dL, subjects will be randomized to their study drug treatment sequence.
 
Sequence of Study Drug Administration
 
  
 Cohort	Period 1	Period 2	Period 3	
   
 1	PRAM9	Regular insulin	Regular insulin + pramlintide	
 
 2	Regular insulin	Regular insulin + pramlintide	PRAM9	
 
 3	Regular insulin + pramlintide	PRAM9	Regular insulin	
 
 4	PRAM9	Regular insulin + pramlintide	Regular insulin	
 
 5	Regular insulin	PRAM9	Regular insulin + pramlintide	
 
 6	Regular insulin + pramlintide	Regular insulin	PRAM9	
  
 
Insulin-to-carbohydrate calculations will be used to identify subject doses. All subjects will get flexible doses of insulin, pramlintide, and PRAM9. See Section 9.1 for complete information on study drug dosing. The dose of regular insulin will be calculated to correspond to a ratio of 9 µg of pramlintide for every 1 unit of insulin. Additionally, the dose of regular insulin will be calculated from the subject's insulin-to-carbohydrate (I:C) ratio to match a 75-gram carbohydrate challenge. Rule 450 will be used for carbohydrate counting and insulin dose calculation in this study (see Appendix 3).
	Cohort	Period 1	Period 2	Period 3	1	PRAM9	Regular insulin	Regular insulin + pramlintide	2	Regular insulin	Regular insulin + pramlintide	PRAM9	3	Regular insulin + pramlintide	PRAM9	Regular insulin	4	PRAM9	Regular insulin + pramlintide	Regular insulin	5	Regular insulin	PRAM9	Regular insulin + pramlintide	6	Regular insulin + pramlintide	Regular insulin	PRAM9
Cohort	Period 1	Period 2	Period 3																										
1	PRAM9	Regular insulin	Regular insulin + pramlintide																										
2	Regular insulin	Regular insulin + pramlintide	PRAM9																										
3	Regular insulin + pramlintide	PRAM9	Regular insulin																										
4	PRAM9	Regular insulin + pramlintide	Regular insulin																										
5	Regular insulin	PRAM9	Regular insulin + pramlintide																										
6	Regular insulin + pramlintide	Regular insulin	PRAM9																										


Prior to study drug administration, a peripheral catheter for blood sampling will be placed into a vein ideally located within the antecubital fossa. The hand of the arm used for blood sampling will be kept warm by use of a heated hand box to increase blood flow and achieve “arterialized” samples. The subject will remain supine and kept warm and be allowed to drink only water (ad libitum).
 
Once the catheter and hand box are in place, study drug(s) will be administered SC over 1 to 3 seconds to the abdomen (around the umbilicus). Co-administered regular insulin plus pramlintide injections should be administered to opposite sides of the abdomen (ie, left and right peri-umbilicus, opposite quadrants). Injection sites should be rotated to avoid injecting at a previously used site.
 
To monitor for hypoglycemia, BGM will be performed in real time at each subject's bedside at 10, 20, 30, 40, 50, 60, 90, 120, and 180 minutes post dosing at Visit 2 through 4.
 
To evaluate drug PD (plasma glucose response) and PK (plasma insulin/pramlintide concentrations), blood samples are to be drawn at the time points described in the Schedule of Assessments (Table 2).
 
Within 2 minutes after the 30 minutes post-dose blood draw, a standardized 75-gram oral glucose challenge should be ingested (within 5 to 10 minutes) by the subject.
 
After the last blood collection (at 360 minutes post-study drug administration), subjects are to be provided a regular meal and insulin (per investigators' discretion).
 
Injection sites will be evaluated by the investigator using the modified Draize scale (Appendix 1) and subjects will complete injection site discomfort questionnaires (Appendix 2).
 
A subject may be discharged from the clinic, per investigator's criteria, when the following has occurred:
 
 • Subject has consumed their meal • Subject has returned to their usual medication regimen, including insulin • Subject's capillary glucose concentration is confirmed to be > 100 mg/dL • Subject is considered medically stable 
Any time during the visit if hypoglycemia occurs (ie, blood glucose < 70 mg/dL), the subject will be rescued with IV dextrose using the following formula to calculate the dose of dextrose:
 $\text{D50\% mL} = (100 \text{ minus BG}) \times 0.4$ 
Where D50% = the dose of IV dextrose, mL = the volume of dextrose, BG = the subject's hypoglycemic blood glucose value
 
The dose of dextrose should be administered slowly, over 2 to 5 minutes.
 
If D50% is administered, then blood glucose will be remeasured by blood glucose meter at 10, 20, and 30 minutes following the end of administration of IV dextrose. Successful plasma glucose recovery should be confirmed (ie, glucose returns to ≥ 70 mg/dL) and the subject medically stabilized. When the subject is medically stable, they can be discharged from the clinic (per criteria above).
 
After a first washout period of 7 to 11 days, subjects will return to the clinic for Treatment Period 2 (Visit 3) and the treatment visit procedures will be repeated

--

	
with each subject crossed over to the next randomized study drug treatment sequence. Upon check-in and completion of morning activities, the subject will receive their second administration of study drug(s).
 
After a second washout period of 7 to 11 days, subjects will return to the clinic for Treatment Period 3 (Visit 4) and the treatment visit procedures will be repeated with each subject crossed over to the last randomized study drug treatment sequence. Upon check-in and completion of morning activities, the subject will receive their third administration of study drug(s).
 
During the Treatment Periods, subjects will undergo symptom-directed PEs, vital sign measurements, AE assessments, concomitant medication assessments, and pregnancy testing for females of childbearing potential.
 
Follow-Up
 
A Follow-up Visit (Visit 5) will be conducted 7 to 11 days after the subject's last dose of study drug(s). Subjects will return to the clinic and undergo complete PE, vital sign measurements, weight measurements, sample collection for hematology and chemistry, AE assessments, concomitant medication assessments, and pregnancy testing for females of childbearing potential.

Number of subjects	Approximately 48 subjects may need to be screened in order to obtain 18 randomized subjects (3 subjects per treatment sequence).
Diagnosis and main entry criteria	
Inclusion criteria:
 
Subjects must meet the following criteria to be included:
 
 1. Understands the study procedures, alternative treatment available, and risks involved with the study, and voluntarily agrees to participate by giving written informed consent 2. Male or non-pregnant, non-lactating female diagnosed with T1D for at least 24 months prior to Screening. 3. Aged 18 to 64 years of age, inclusive 4. On a stable insulin regimen for 21 days prior to Screening (no greater than $\pm 20\%$ variability in total daily dose) 5. Have a plasma C-peptide level < 0.6 ng/mL at Screening 6. Have an HbA1c $< 10\%$ at Screening 7. Body mass index (BMI) in the range of ≥ 18 to ≤ 35 kg/m² at Screening 8. For women of childbearing potential, there is a requirement for a negative urine pregnancy test at Screening and for agreement to use contraception throughout the study and for 7 days after the last dose of study drug. 
Acceptable contraception includes birth control pill/patch/vaginal ring, Depo-Provera® (medroxyprogesterone acetate), Norplant® System (levonorgestrel), an intra-uterine device (IUD), the double barrier method (the woman uses a diaphragm and spermicide and the man uses a condom), or abstinence.
 
 9. Fasting Serum Triglycerides concentration < 200 mg/dL
	
Exclusion criteria:
 
Subjects meeting any of the following criteria are to be excluded. Laboratory criteria will be based on testing performed at the Screening Visit.
 
 1. Currently being treated with pramlintide or has discontinued pramlintide within 21 days of Screening 2. Currently using an insulin pump

	
 3. Has renal insufficiency (serum creatinine > 3.0 mg/dL) or end-stage renal disease requiring renal replacement therapy 4. Has hepatic disease, including serum ALT or AST \geq 3 times the upper limit of normal (ULN) 5. Has hepatic synthetic insufficiency (serum albumin < 3.0 g/dL) 6. Has a hematocrit value that is exclusionary, as shown below: 
 a. Female <35.5% b. Male <38.3% 7. Has a hemoglobin value that is exclusionary, as shown below: 
 a. Female <11.5 g/dL b. Male <12.5 g/dL 8. Has out-of-range systolic or diastolic BP readings at Screening (systolic BP < 90 or > 150 mm Hg or diastolic BP < 50 or > 100 mm Hg) 9. Has clinically significant ECG abnormalities at Screening 10. Has congestive heart failure, NYHA Class III or IV 11. Has history of myocardial infarction, unstable angina, or revascularization within 6 months prior to Screening 12. Has history of a cerebrovascular accident in 6 months prior to Screening with major neurological deficits 13. Has active malignancy within 5 years prior to Screening (exception: basal cell or squamous cell skin cancers) 14. Has had major surgical operation within 60 days prior to Screening or planned surgical operation during the study 15. Has a seizure disorder (other than with suspected or documented hypoglycemia) 16. Has a current bleeding disorder, treatment with anticoagulants, or platelet count < $50 \times 10^9/L$ 17. Has a history of allergies or significant hypersensitivity to pramlintide or any pramlintide-related products or to any of the excipients in the investigational formulation 18. Has a history of positive test result for hepatitis B virus (HBV), hepatitis C virus (HCV), or human immunodeficiency virus (HIV) 19. Has a concurrent illness not controlled by a stable therapeutic regimen 20. Tests positive for drugs of abuse at Screening. Subjects testing positive for tetrahydrocannabinol (THC) at Screening or reporting active marijuana use will be allowed to participate in the study at the discretion of the investigator. 21. Has active substance or alcohol abuse (> 21 drinks/week for males or > 14 drinks/week for females). 22. Has participated in other studies involving administration of an investigational drug within 30 days or 5 half-lives prior to Screening (whichever is longer) or during participation in the current study. 23. There is any reason the investigator deems exclusionary 24. Has donated blood within 8 weeks prior to Screening.
--	--

Study drug, dosage, and administration	PRAM9 , a pramlintide-regular insulin co-formulation Dose: See Sections 9.1.3 and 9.1.4 for a full description of pramlintide dose adjustment. Route of administration: SC (in the abdomen, peri-umbilicus)
Active Controls, dose, and route of administration	Regular insulin: Humulin® R (U-100) (regular insulin human injection) Dose: See Section 9.1.2 . Route of administration: SC (in the abdomen, peri-umbilicus)
	Regular Insulin plus pramlintide (co-administered as separate injections) Dose: See Sections 9.1.3 and 9.1.4 for a full description and pramlintide dose adjustment. Route of administration: SC (in the abdomen, peri-umbilicus). The separate, co-administered regular insulin and pramlintide injections should be given to opposites sides of the abdomen (ie, left and right peri-umbilicus, opposite quadrants).
Duration of subject participation and duration of study	Screening Phase of up to 4 weeks; Treatment Periods of up to 3 weeks; and 7 to 11 days of follow-up. The estimated duration of subject participation is 8 weeks.
Concomitant medications	All medications taken within 28 days before the first study treatment visit (Day 1), including insulin, will be documented in the electronic case report form (eCRF). Any changes to a subject's concomitant medication regimen after the first treatment on Day 1 will also be documented in the eCRF. Ideally, subjects should be on a stable regimen of all concomitant medications except insulin for at least 28 days prior to Screening, and they will be encouraged to avoid making changes (excepting insulin) to their concomitant medication regimen during participation in the study. In addition, investigators are encouraged to avoid adding to or changing a participant's medications during study participation unless deemed medically necessary.
	Diabetes Medication Subject diabetes medication will be recorded on the day of Screening: 
 • Total daily meal-time insulin 
 ○ Type of insulin (regular insulin, lispro, or aspart) • Basal insulin 
 ○ Type of insulin (glargine, detemir, or degludec) • Total daily dose of insulin • Glucagon-like peptide-1 (GLP-1) analogue
Safety assessments	Safety assessments include reporting of AEs and SAEs, vital sign measurements, clinical safety laboratory evaluations, and reasons for treatment discontinuations due to toxicity. In addition, the investigator will use a modified Draize scale to evaluate the injection sites after each administration for signs of erythema and edema (Appendix 1) and subjects will complete questionnaires to assess injection site discomfort (Appendix 2).

	
To monitor for hypoglycemia, BGM will be performed in real time at each subject's bedside at 10, 20, 30, 40, 50, 60, 90, 120, and 180 minutes post dosing at Visit 2 through 4.
 
Safety assessments will be performed at specified time points. Vital sign measurements, including BP, HR, respiratory rate, and temperature will be taken after \geq 5 minutes of seated rest.
 
The AE reporting period for a subject enrolled in the study begins when the subject provides informed consent and is continued through the Follow-Up Visit. All AEs that occur in subjects during the AE reporting period must be recorded, regardless of the relationship of the AE to study drug. All AEs are to be followed until resolution or the subject is medically stable.

Pharmacodynamics	
At Visits 2, 3, and 4, samples will be drawn to measure plasma glucose levels. Venous blood samples will be drawn 10 ± 2 minutes before and immediately prior to dosing (-2 to 0 minutes), and then 10, 20, 30, 40, 50, 60, 90, 120, 150, 180, 240, 300, and 360 minutes post-dosing (window allowance of ± 2 minutes).
 
Plasma glucose levels will be used to calculate the following PD parameters: C_{max}, T_{max}, area over the curve (AOC), and AUC (see Section 13.3.2).

Pharmacokinetics	
At Visits 2, 3, and 4, samples will be drawn to measure plasma insulin and pramlintide levels. Venous blood samples will be drawn 10 ± 2 minutes before and immediately prior to dosing (-2 to 0 minutes), and then 10, 20, 30, 40, 50, 60, 90, 120, 150, 180, 240, 300, and 360 minutes post-dosing (window allowance of ± 2 minutes).
 
Insulin and pramlintide concentrations will be used to calculate the following PK parameters: C_{max}, T_{max}, AUC_{0-90}, AUC_{0-180}, and AUC_{0-360}

Statistical methods	Complete details for the statistical analyses are included in a separate Statistical Analysis Plan (SAP).

Table 2: Schedule of Assessments

Study Phase	Screening	Treatment Period			Follow-Up
		Period 1 V2	Period 2 V3	Period 3 V4	
Study Visit	V1				V5
Study Day	-28 to -1	1	(V2+7-11 days) ¹⁴	(V3+7-11 days) ¹⁴	(V4+7-11 days) ¹⁴
Informed consent	X				
Medical history & demographics	X				
Inclusion/exclusion review	X				
Urine drug screen ¹	X				
Physical exam & body weight ²	X	X	X	X	X
Height	X				
12-lead ECG	X				
Vital sign measurements ³	X	X	X	X	X
Hematology	X				X
Clinical chemistry	X				X
C-peptide & HbA1c	X				
Urine pregnancy test	X	X	X	X	X
IV catheter placement		X	X	X	
Clinic admission/discharge ⁴		X	X	X	
Overnight fast from midnight		X	X	X	
Blood glucose measurement (BGM) ⁵		X	X	X	
Randomization ⁶		X			
Study drug(s) injection(s) ⁷		X	X	X	
PK collection ⁸		X	X	X	
PD collection ⁹		X	X	X	
Draize scales ¹⁰		X	X	X	
Injection site discomfort ¹¹		X	X	X	
Oral glucose administration ¹²		X	X	X	
Meal ¹³		X	X	X	
Review AEs		X	X	X	X
Concomitant medications	X	X	X	X	X

AE = adverse event; ECG = electrocardiogram; PD = pharmacodynamics; PK = pharmacokinetics; V = visit

- 1) **Urine Drug Screen:** To include cocaine, THC, opiates, amphetamines, methamphetamine, and phencyclidine.
- 2) **PE:** Full PE (excluding breast, pelvic, rectal, and genitourinary systems) to be performed at Screening and Follow-Up Visits; includes height at Screening. Symptom-directed PEs to be performed at Visits 2, 3, and 4.

- 3) **Vital signs:** Temperature, respiration, HR and BP (after 5 minutes seated rest) to be performed at all visits. During injection visits, HR and BP measurements to be repeated 30 ± 5 minutes, 180 ± 5 , and 360 ± 5 minutes post-dose.
- 4) **Admission and discharge:** Arrival for an overnight stay at the clinical research facility on the day prior to treatment visits. Subject to be discharged the next day after study procedures have been performed and after the following have occurred: 1) subject has consumed their meal; 2) subject has returned to their usual medication regimen [including insulin]; 3) capillary glucose concentration is confirmed to be > 100 mg/dL; and 4) subject is considered medically stable.
- 5) **Blood glucose measurement (BGM):** BGM will be performed in real time at each subject's bedside at 10, 20, 30, 40, 50, 60, 90, 120, and 180 minutes post dosing at Visit 2 through 4. Prior to dosing, a capillary blood sample will be tested to confirm that blood glucose is in the range of 80 to 150 mg/dL. If result is > 150 mg/dL after repeat test, the visit should be rescheduled after a minimum 24-hour wait. If the blood glucose is > 150 mg/dL after repeat test, then the investigator may treat with a bolus dose of IV regular insulin, per discretion, to bring the subject into the required blood glucose range. Before initiating study treatment, at least 40 minutes should have passed from the last dose of administered insulin, and the subject's blood glucose level should be within the range of 80 to 150 mg/dL. If the blood glucose is < 80 mg/dL after repeat test, then the investigator may treat with oral glucose tabs/solution or IV glucose, per discretion, to bring the subject into the required blood glucose range. Before initiating study treatment, at least 30 minutes should have passed from the last dose of administered glucose, and the subject's blood glucose level should be within the range of 80 to 150 mg/dL. If hypoglycemia occurs (ie, blood glucose < 70 mg/dL), the subject will be rescued with IV dextrose, according to the formula shown in [Section 8.5, Occurrence of Hypoglycemia](#).
- 6) **Drug sequence randomization:** To be performed just prior to first study drug injection at Period 1 (Visit 2).
- 7) **Study drug administration:** Glucose must be 80 to 150 mg/dL prior to administration of study drug(s). Injection sites should be rotated to avoid injecting at a previously used site.
- 8) **PK:** Venous blood samples will be drawn 10 ± 2 minutes before and immediately prior to dosing (-2 to 0 minutes), and then 10, 20, 30, 40, 50, 60, 90, 120, 150, 180, 240, 300, and 360 minutes post-dosing (window allowance of ± 2 minutes).
- 9) **PD:** Venous blood samples will be drawn 10 ± 2 minutes before and immediately prior to dosing (-2 to 0 minutes), and then 10, 20, 30, 40, 50, 60, 90, 120, 150, 180, 240, 300, and 360 minutes post-dosing (window allowance of ± 2 minutes).
- 10) **Draize scales:** To be performed by the investigator using the modified Draize scale at 30, 90, and 360 minutes (± 2 minutes) post-study drug injection ([Appendix 1](#)).
- 11) **Injection site discomfort evaluation:** To be performed by the subject at 10 and 30 minutes (± 2 minutes) post-study drug injection. Subjects should complete injection site discomfort questions at 10 mins and then Question Q1c is to be answered at 360 mins post-study drug injection ([Appendix 2](#)).
- 12) **Oral glucose Within 2 minutes** of the blood draw at 30 minutes post-dose, a standardized 75-gram oral glucose challenge (eg, 75 grams of glucose syrup and water) should be given to the subject. Subject should consume the solution within 5 to 10 minutes.
- 13) **Meal:** After the last blood collection (at 360 minutes post-study drug administration), subjects will be provided a regular meal and insulin (per investigator's discretion) as per the site's usual practice
- 14) .Previous visit +7 to 11 days.

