6. INVESTIGATIONAL PLAN

6.1. Overall Study Design

This is a randomized, open-label, active-controlled, single-dose, 3-treatment, 3-period, 3-way crossover, comparative PD and PK inpatient study in adults with T1D. The study comprises 5 visits: Screening (Visit 1), Treatment Periods (Visits 2 – 4), and Follow-Up (Visit 5).

To determine eligibility, subjects will complete the Screening procedures (Visit 1) up to 28 days before the first treatment visit (Visit 2). Subjects will be instructed to eat normally and take their usual medications, but to refrain from alcohol for 24 hours prior to checking in for treatment visits.

Treatment Periods

For Treatment Period Visits 2 through 4, eligible subjects will be instructed to arrive for an overnight stay at the clinical research facility on the day prior to each treatment visit. At the clinic, subjects will be given a standardized dinner meal, and instructed to take their prescribed evening mealtime insulin regimen and basal insulin dose. The subjects will fast after midnight but will be allowed to drink water ad libitum (ie, tap water, bottled water, distilled water, etc. [water without carbohydrates]) and take any prescribed medications.

During each Treatment Period Visit, subjects will receive a single SC dose of PRAM9, regular insulin, or co-administered regular insulin plus pramlintide. On the morning of each treatment visit and prior to dosing, a fasting blood sample will be tested using a blood glucose meter (BGM) to confirm that blood glucose is in the range of 80 to 150 mg/dL.

- If the blood glucose is > 150 mg/dL after repeat test, then the investigator may treat with an intravenous (IV) bolus dose of regular insulin, per discretion, to bring the subject into the required blood glucose range. Before initiating study treatment, at least 40 minutes should have passed from the last dose of administered insulin and the subject's glucose level should be within the range of 80 to 150 mg/dL.
- If the blood glucose is < 80 mg/dL after repeat test, then the investigator may treat with oral glucose tabs/solution or IV glucose, per discretion, to bring the subject into the required blood glucose range. Before initiating study treatment, at least 30 minutes should have passed from the last dose of administered glucose and the subject's glucose level should be within the range of 80 to 150 mg/dL.

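### Table 2, note 5 gives two incompatible instructions for a pre-dose glucose above 150 mg/dL, and one of them conflicts with the synopsis and Sections 6.1 and 10.2.2

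*Protocol*

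**What the plan says.** The protocol states the pre-dose glucose check in four places: the synopsis (Methodology), Table 2 note 5, Section 6.1 and Section 10.2.2. All four require 80 to 150 mg/dL before study drug is given.

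For a reading still too high on repeat, note 5 first says: "If result is > 150 mg/dL after repeat test, the visit should be rescheduled after a minimum 24-hour wait". It goes straight on: "If the blood glucose is > 150 mg/dL after repeat test, then the investigator may treat with a bolus dose of IV regular insulin". After that correction, dosing may proceed provided "at least 40 minutes should have passed from the last dose of administered insulin" and glucose is back in range.

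Section 6.1 carries the correction option without the first of those sentences: "then the investigator may treat with an intravenous (IV) bolus dose of regular insulin, per discretion". The synopsis and Section 10.2.2 do the same. All three then set the condition for deferral, which is that the subject's glucose "cannot be optimized to 80 to 150 mg/dL within 2 hours, then the visit should be rescheduled after a minimum 24-hour wait", per the investigator's discretion. Note 5 has no 2-hour condition.

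**The concern.** A single finding, glucose above 150 mg/dL after a repeat test, leads to two different actions. Under the first sentence of note 5 the subject is not dosed that morning. Under the second sentence, and under the three other statements, the subject may be corrected and dosed at the same visit.

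The crossover comparison depends on the three periods being run alike within each subject. Deferred subjects come back for another morning, whereas corrected subjects are dosed with recent intravenous regular insulin on board. That could bear on three things:

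- baseline glucose;
- measured plasma insulin, whose AUC and Cmax are secondary endpoints (Section 13.3.2);
- the primary endpoint, the 0 to 180 minute area for plasma glucose above 180 mg/dL (Section 5.3).

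The study is open-label at up to 4 sites. Sequence is assigned at Visit 2 after glucose is confirmed in range, so the choice there cannot depend on assignment. At Visits 3 and 4, staff can know the next treatment when choosing between the two instructions.

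Whichever action a site takes, it departs from one written sentence. Protocol deviations on this point therefore cannot be classified consistently.

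**Working it through.** No sample-size or power figure is involved. The check sets the four statements side by side for the same trigger, above 150 mg/dL after repeat test.

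| Place in the protocol | IV regular insulin, then dose after at least 40 minutes if in range | Reschedule outright, at least 24 hours | Reschedule only if not in range within 2 hours |
|---|---|---|---|
| Synopsis, Methodology | yes | no | yes |
| Table 2, note 5 | yes | **yes** | **no** |
| Section 6.1 | yes | no | yes |
| Section 10.2.2 | yes | no | yes |
| Count | 4 of 4 | 1 of 4 | 3 of 4 |

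1. **Same trigger.** Both sentences of note 5 use the same threshold and the same repeat-test condition, so they do not describe different cases.

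2. **No link between them.** In the other three places, correction comes first and deferral follows only if it fails within 2 hours. That condition is what makes the two actions compatible. Note 5 omits it and puts deferral first, so nothing orders its two sentences.

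3. **No order of precedence.** Section 10 refers sites to Table 2 for the schedule of procedures. The protocol text shown does not say whether the table or the body prevails.

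4. **Low readings.** For values below 80 mg/dL, note 5 gives the same correction route as the other places but again leaves out the 2-hour limit. This is an omission and not a contradiction.

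5. **Visit windows.** Visits 3 and 4 fall 7 to 11 days after the previous visit. A visit due on day 11 and deferred by at least 24 hours falls on day 12 or later, outside the window. Any deferral carries this risk. The first sentence of note 5 would apply it to every confirmed high reading, and not only to failed corrections.

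6. **How often it could arise.** There are 18 subjects × 3 periods = 54 planned dosing mornings. The protocol gives no rate of pre-dose readings above 150 mg/dL, so 54 is only an upper limit.

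The 40-minute and 24-hour intervals run from different starting points: the last insulin dose, and the abandoned visit. They show that the two routes differ but do not measure an effect on the data.

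**The case against.** The strongest reply is that this is one stray sentence. Three full statements agree on a complete sequence, the rest of note 5 follows it closely, and Section 10.2.2, the detailed procedure for the dosing day, is clear. A site reading the whole note meets the correction option in the next sentence. Note 5 could also be read as a default (*should*) followed by a discretionary option (*may*).

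That reading softens the clash inside the note but does not remove the clash with the rest of the protocol. Note 5 would then make deferral the default, while the other three places make it the fallback after a failed correction. Sites are also sent to the table.

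The objection on impact largely stands. Every route to dosing requires 80 to 150 mg/dL, and at least 40 minutes after any correction insulin. Two pre-dose samples are taken. Intravenous insulin before dosing is permitted in all four statements, and Section 10.2.1 allows it overnight to hold the same range, which should make high morning readings less common. Correction and rescheduling are discretionary in the body text too, so some variation would remain even after note 5 is corrected. No direction or size of bias can be shown.

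**Conclusion.** The contradiction is real and certain on the text. Note 5 conflicts with itself and with the synopsis, Section 6.1 and Section 10.2.2, and it alone lacks the 2-hour condition. It concerns an operative rule for the dosing morning, so it should be fixed, although it does not undermine the design.

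The effect on the primary endpoint and the insulin pharmacokinetics is possible but unquantified. It depends on how often readings above 150 mg/dL occur and on how sites resolve the conflict, and the protocol gives information on neither. What can be said is that the conflict adds avoidable variation between subjects and periods, on at most 54 mornings, and is not the only source of pre-dose insulin exposure.

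**What to change.** Reconcile note 5 of Table 2 with the synopsis, Section 6.1 and Section 10.2.2 so that one instruction applies to a pre-dose glucose above 150 mg/dL after repeat test. The 2-hour condition, for high and low readings alike, should be either present in all four places or absent from all four. Which clinical rule applies is for the sponsor to decide; this review takes no position.

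If the sponsor keeps the rule now in the other three places, the change is an edit to one table note in a protocol clarification. If it chooses the first sentence of note 5 instead, the other three places need editing as well. Neither requires new data, visits or samples.
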